#### Steroid Assays:

Blood for estradiol and progesterone will be obtained on each test day and sent to as yet to be determined laboratory for assaying via HPLC with Tandem Mass Spectrometry. The lower limit of detection is 1 pg/ml for estradiol and 0.1 ng/ml for progesterone. Intra-assay coefficient of variation (CV) for samples with mean estradiol level of 1.06 ng/dl is 2.27%, for inter-assay precision, the CV is 4.36% for mean estradiol level of 1.08 ng/d.

#### 2. Specimens

Not applicable.

# 3. Genetic Testing

Per above, we will obtain 10 cc whole blood for the study of genes related to estrogen metabolism and the neurochemical targets of estrogen. These include, but may not be limited to serotonin, acetylcholine, dopamine, glutamate, and norepinephrine neurotransmitter systems. Our goal is to interrogate functional polymorphisms which are linked to the regulation of mood and cognition and link these to possible effects of estrogen on these behaviors. We are not examining genes in relation to psychiatric disorders in this sample as all subjects included in this study are without previous or present psychopathology.

Repeated measures analysis of variance (ANOVA) will then be performed to test interaction of TRP depletion and ERT on brain activation patterns and simple effects analyses will reveal overall effects of estrogen or TRP depletion.

Other Analyses: Effects of TRP depletion and ERT on cognitive performance and mood will be assessed using random effects, mixed models. Repeated measures ANOVA will be used to assess the effects of TRP depletion on free and total plasma TRP levels. The relationship between behavioral ratings and cognitive performance and plasma TRP levels will be assessed using bivariate correlational methods.

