#### OBJECTIVES

**Specific Aim 1:** To replicate and extend our previous behavioral findings of an interaction between ET and TRP-D on verbal memory in a group of early menopausal women randomized to receive ET (n=28). In a previous behavioral study of TRP-D and ET in healthy menopausal women (Amin et al., 2006b), we observed that TRP-D interfered with verbal memory to a lesser extent following ET than before. *In a new sample of women, we again hypothesize* (**H1.1**) *that paragraph recall performance and verbal paired-associates learning will decline as a result of TRP-D, but that ET will attenuate this decline.* In our previous study, we also found that length of hypogonadism (measured by months since last

menstrual period) was significantly associated with waning verbal memory performance. However, we did not have sufficient power with 18 women to detect whether the magnitude of ET effects differed based on length of time since menopause. *In this larger sample of 28 women, we hypothesize* (H1.2) *that women who have more recently experienced menopause will benefit more from ET than later menopausal women.* 

**Specific Aim 2:** To evaluate the extent to which effects of ET and TRP-D on verbal working memory are mediated through the dorsolateral prefrontal cortex. Previous neuroimaging studies have associated ET with improved working memory performance and increased dorsolateral prefrontal cortex (DLPFC) activation (Duff & Hampson 2000; Shaywitz et al., 1999). However, it is unclear whether TRP-D has an effect on working memory (Harrison et al., 2004; Riedel et al., 2003). It is hypothesized (**H2.1**) that ET will increase DLPFC activation during working memory more so than PT, but there will be no effect of TRP-D and no interaction between estrogen and serotonin effects in either the ET or PT groups. Very few fMRI studies have examined the impact of practice or rescanning on behavioral measures or the BOLD response during cognitive tasks. We seek to fill that void with the proposed study by including a placebo arm. Since submission of the A2 application, we have obtained test-retest data from our MR colleagues ([name], Ph.D.) demonstrating that with our new sample size of 28 women receiving ET and 14 women receiving placebo we can adequately test our hypothesis regarding ET and TRP-D effects on DLPC activation during the proposed working memory task.

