# TRP Depletion Tests:

Each of the four test days will begin in the morning, no later than 7:30 AM, following an overnight fast that begins at midnight and subjects will remain fasting until the end of the test session, approximately 8hours. Subjects will be admitted to a specially designated testing room on the CHPS/PCWBW and will remain in the test room for most of the session, but will be free to walk about the room and the CHPS/PCWBW, use the facilities, and drink water. They will be continuously monitored throughout the day by a trained research nurse, with a medical research investigator available at all times.

Baseline behavioral ratings, blood samples, and vital signs will be taken from 7:30 - 8:00 AM. Initial assessments include measurement of sleep quality (PSQI; test days 2 and 4 only), and hot flash severity (daily diary completed for previous 7 days). Mood will be evaluated using the HAM-D, BDI, POMS, STAI, PSS and VAS. Blood sampling in the morning on each test day will measure estradiol, progesterone, serum hormone binding globulin, DHEA, and baseline tryptophan (total and free) levels. Additionally, on the first test day only, one additional tube of blood will be drawn to examine genetics of estrogen synthesis and metabolism and genes for neurochemicals/systems modulated by estrogen and Version: November 28, 2016 IRB APPLICATION page 18 of 35

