Approximately 5.5 hours following ingestion of the 70 capsules, participants will repeat evaluations of mood and undergo cognitive testing (1:30 - 2:00 PM). Immediately prior to the fMRI scan (2:30 PM), a second blood draw will be conducted to measure changes in free and total tryptophan. Participants will then be escorted to CAMRIS for performance of cognitive tasks while in a 3T MR scanner. Immediately prior to entering the scanner, all participants will submit a urine sample for toxicology and urine pregnancy tests, as required by CAMRIS. The scan will begin approximately 6.5 hours following ingestion of capsules. After the end of the test session, a regular diet will be resumed. We will provide a light lunch to all participants prior to discharging them at the end of the test day.

The second TRP depletion test will be administered 1-week after the first. If subjects were randomized to receive the capsules filled with 31.5 g of lactose/microcellulose (sham depletion) during the first depletion sequence, they will receive capsules filled with amino acids (active depletion) during the second sequence (and vice versa). The clinicians conducting the study and the subjects in the study will be blind to which mixture the subject is receiving in the capsules. Following approximately *6-weeks* of ET, another pair of test days will be scheduled one week apart, one sham and one active.

\*In cases where participants do not fully complete a test day before being randomized to the study drug, they will have the option to repeat the unsuccessful test day in full.

\*\*If subjects cannot commit to completing test days Monday through Friday, there is an option to complete scans on weekends. These participants will not be utilizing the services of the CHPS and will instead be monitored by a study MD during their test day instead of CHPS nurse. These women will report to [name] and will complete the test day exactly as described above, with the

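### The plasma TRP correlations name no unit of analysis and no adjustment for depletion condition, although each woman has two sham and two active test days

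*Combined protocol and SAP*

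**What the plan says.** Section 4, Statistical Analysis, paragraph Other Analyses, has three consecutive sentences on non-imaging data.

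- Depletion and estrogen effects on outcomes: "Effects of TRP depletion and ERT on cognitive performance and mood will be assessed using random effects, mixed models".
- Depletion effect on TRP itself: "Repeated measures ANOVA will be used to assess the effects of TRP depletion on free and total plasma TRP levels".
- TRP against outcomes: "The relationship between behavioral ratings and cognitive performance and plasma TRP levels will be assessed using bivariate correlational methods".

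The first two methods allow for repeated measurement of the same woman. The third names no such allowance.

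The data structure is set out under TRP Depletion Tests. "Each of the four test days will begin in the morning", and after the treatment period "another pair of test days will be scheduled one week apart, one sham and one active"; the pre-treatment pair is built the same way. On each day TRP is sampled in the morning, and shortly before the scan "a second blood draw will be conducted to measure changes in free and total tryptophan". In the afternoon "participants will repeat evaluations of mood and undergo cognitive testing". Specific Aim 2 under Objectives gives the sample size: "with our new sample size of 28 women receiving ET and 14 women receiving placebo".

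**The concern.** An ordinary correlation test assumes independent pairs. Here one woman supplies four pairs, and the experiment itself moves TRP between them. The sentence leaves open whether all days are pooled, each day is analysed alone, or each woman is reduced to a change score. It also does not say which TRP value (morning, pre-scan or change; free or total) is used. These choices answer different questions and have different error rates, and nothing stops the choice from being made after the data are seen.

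Two things are at stake if days are pooled. The p-value is wrong because of clustering. The correlation also absorbs the sham/active contrast: hypothesis H1.1 expects depletion to worsen verbal memory, and depletion lowers TRP by design, so the two would correlate across days even if the size of a woman's TRP fall said nothing about her memory.

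**Working it through.** **Inputs from the documents.** 28 + 14 = 42 women; m = 4 test days (2 sham, 2 active); 42 × 4 = 168 woman-days. The plan gives no power, alpha or sample-size figure for these correlations, so there is no stated figure to reproduce.

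**Assumed, because the documents do not give them.** Two-sided alpha of 0.05; intraclass correlation (ICC) of TRP 0.3-0.8 and of the outcome 0.5-0.8; TRP drop on active days d = 0, 2, 3 or 4 within-condition SD.

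**Step 1. Size of a pooled Pearson test with no TRP-outcome relation.**

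- Effective TRP ICC, counting the sham/active contrast: E = (ICC_TRP − d²/12) / (1 + d²/4)
- Variance inflation: DE = 1 + (m − 1) × E × ICC_outcome
- Type I error = 2 × [1 − Φ(1.96/√DE)]

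Example, d = 0, ICCs 0.5/0.5: DE = 1 + 3 × 0.5 × 0.5 = 1.75, error 13.8%.
Example, d = 4, ICCs 0.5/0.5: E = (0.5 − 1.333)/5 = −0.167; DE = 1 − 3 × 0.167 × 0.5 = 0.75, error 2.4%.

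| TRP drop (SD) | ICC TRP / outcome | E | DE | Formula | Simulated |
|---|---|---|---|---|---|
| 0 | 0.3 / 0.5 | 0.300 | 1.450 | 10.4% | 10.1% |
| 0 | 0.5 / 0.5 | 0.500 | 1.750 | 13.8% | 13.6% |
| 0 | 0.7 / 0.7 | 0.700 | 2.470 | 21.2% | 21.2% |
| 0 | 0.8 / 0.8 | 0.800 | 2.920 | 25.1% | 26.1% |
| 2 | 0.3 / 0.5 | −0.017 | 0.975 | 4.7% | 5.0% |
| 2 | 0.7 / 0.7 | 0.183 | 1.385 | 9.6% | 9.0% |
| 3 | 0.3 / 0.5 | −0.138 | 0.792 | 2.8% | 3.3% |
| 3 | 0.5 / 0.5 | −0.077 | 0.885 | 3.7% | 4.1% |
| 3 | 0.8 / 0.8 | 0.015 | 1.037 | 5.4% | 5.2% |
| 4 | 0.5 / 0.5 | −0.167 | 0.750 | 2.4% | 2.5% |
| 4 | 0.5 / 0.8 | −0.167 | 0.600 | 1.1% | 1.1% |

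Simulations used 42 women × 4 days and 10,000 trials per row (6,000 for the 3 SD rows and the 0.8/0.8 rows). With both ICCs zero, the simulated size was 4.8-5.0%. With 28 women the pattern was the same.

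**Step 2. Confounding by condition.** Let depletion shift the outcome by e = 0.5 SD, with TRP unrelated to the outcome within condition. The expected pooled correlation is

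r = (d·e/4) / √[(1 + d²/4)(1 + e²/4)].

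- d = 2: 0.25/√(2 × 1.0625) = 0.17
- d = 3: 0.375/√(3.25 × 1.0625) = 0.20
- d = 4: 0.5/√(5 × 1.0625) = 0.22

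The significance threshold with 168 pairs is about 1.96/√168 = 0.15, so the expected value is already past it. Simulated rejection was 62% (2 SD), 76-78% (3 SD) and 86% (4 SD).

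**Step 3. Alternatives on the same data, 42 women.**

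| Analysis | No relation | Condition shifts the outcome only |
|---|---|---|
| Within-woman, no condition term | 4.7-5.3% | 97-99% |
| Within-woman, adjusted for test day/condition | 4.6-5.2% | 5.0-5.6% |
| Single test day, one pair per woman | 4.6-5.3% | 4.8-5.1% |
| One sham-to-active change score per woman | 4.7-5.3% | 5.0% |

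Allowing for the woman alone does not remove the confounding; the condition term is essential.

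**Step 4. Per-day correlations.** Four tests per outcome at 5% give 1 − 0.95⁴ = 18.5% if independent (at most 4 × 5% = 20%), before counting free and total TRP and the several scales.

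**The case against.** The strongest reply is that the plan nowhere says days will be pooled. A correlation within one test day, or of one change score per woman, is also bivariate and keeps its 5%. This stands. A reader might infer that the planned method gives wrong error rates as such; the documents do not support that. What they support is an unstated unit of analysis, one natural reading of which is invalid.

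A second reply is that inflation of 10-26% needs TRP to be equal on sham and active days, although the procedure exists to lower it. This also stands. Those rows fit morning values, taken before the capsules. For pre-scan values on all four days they are an upper bound, and with a large drop the pooled test is conservative.

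A reader might also infer that the trial loses power to detect depletion effects. It does not: the mixed models and the repeated measures ANOVA in the same paragraph already test that contrast, and they use the within-woman comparison.

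Finally, none of the numbered hypotheses rests on a TRP-outcome correlation. That is correct and limits the weight of the point. It does not remove it, because the sentence still permits a pooled result that restates the sham/active contrast.

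**Conclusion.** The point holds in conditional form. The plan specifies neither the unit of analysis nor an adjustment for depletion condition, and the two sentences before it show that suitable methods were at hand. If days are pooled as independent, the type I error is about 10-26% with no TRP drop, 5-9% at 2 SD, 3-5% at 3 SD and 1-2.5% at 4 SD. The more serious consequence is confounding: a 0.5 SD depletion effect alone would make the pooled correlation significant in about 62-86% of trials. Per-day correlations avoid both problems but bring several tests per outcome with no multiplicity rule.

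All these sizes rest on assumed ICCs, TRP drops and a two-sided 5% level. The dependence on pooling and on condition does not rest on any one of those values. The tests of the main hypotheses are unaffected.

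**What to change.** Replace the sentence with one of two prespecified analyses.

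- **Preferred:** a mixed model for each outcome with a random intercept for woman; depletion condition, treatment arm and pre/post phase as factors, with their interactions because H1.1 expects estrogen to change the depletion effect; and TRP split into the woman's mean and her day-specific deviation. The coefficient on the deviation is the within-woman TRP-outcome relation.
- **Simpler:** correlate one sham-minus-active change score in TRP with the matching change in the outcome, one pair per woman. Analyse the pre- and post-treatment pairs separately or average them; do not stack them as independent.

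In either case, state which TRP measure is used (free or total; pre-scan level or change from morning), name the few outcomes of interest, and give a multiplicity rule or label the results as exploratory. The cost is SAP wording and minor programming. No new data are needed.

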# **RISK/BENEFIT ASSESSMENT**

# 1. Risks

Treatment with Estrogen: The reported adverse reactions to estrogen treatment include nausea, vomiting, breast tenderness or enlargement, enlargement of benign tumors of the uterus, retention of excess fluid, spotty darkening of the skin, and vaginal bleeding. An increased risk of stroke or blood

clots is present from the beginning of estrogen administration, but long-term estrogen treatment (more than 5 years) may increase the risk of cardiovascular events, gallbladder disease, and dementia. Most recently, estrogen treatment alone was not associated with an increased risk of breast carcinoma. Serious side effects will be minimized by short-term treatment, exclusion of women who would be at heightened risk and careful monitoring of the treatment.

Progesterone Treatment: Adverse effects of progesterone (Prometrium) or medroxy progesterone include breast tenderness, bloating, fluid retention, and depression. In addition, findings from recent studies suggest that long-term (at least 5 years) progesterone treatment increases the risk of breast cancer, possibly more so than estrogen. Women who participate in this study must have had a normal mammogram within the previous 12 months. In addition, short-term treatment will limit the risks associated with progesterone administration.

Tryptophan depletion test: The risks associated with ingestion of the amino acid mixture include increased depression, nausea, vomiting, and diarrhea. The symptoms are transient and usually resolve within 24 hours.

Fasting: Subjects are required to abstain from eating from mid-night to approximately 3:30 pm on test days. Individuals will take the capsules in the morning per above and may drink clear fluids and coffee or tea without dairy or sugar. During fasting individuals are likely to experience hunger, and possibly a mild headache and irritability. The headache usually improves upon eating after the scan session but may continue into the evening, particularly if no anti-inflammatory medications are taken.

Lactose: Subjects who suffer from extreme lactose intolerance will not be allowed to participate in this study. Extreme lactose intolerance is described as a history of severe abdominal discomfort or cramping up after eating or drinking food products that contain lactose. However, subjects who describe themselves as having mild to moderate lactose intolerance will be given microcellulose capsules instead of lactose when randomized to sham depletion.

fMRI: fMRI conducted at 3 T has not been associated with any adverse medical effects. The principal anticipated difficulty is feelings of claustrophobia associated with all MR imaging of the head. All subjects will be screened for the presence of any metallic objects that they may be holding or have implanted in their bodies, and all potential subjects with metallic implants will be excluded. This questionnaire will be repeated prior to imaging to insure that they are not bringing any metallic materials into close proximity of the magnet, where they might be pulled toward the magnet or heated by the magnet. It is also possible participants may experience a slight metallic taste in their mouths either during or after the scan. They may also experience slight dizziness after coming out of the scanner or have a slight headache following their scan.

EXPERIMENTAL DEVICE CLAUSE: Some of the pulse sequences and/or RF coils are not FDA approved but are considered non-significant risk investigational devices.

Incidental Findings: There is also a risk that during the course of this study, an unexpected finding may be observed in MRI scans, even though the scans are not intended for clinical purposes. These findings or abnormalities are termed "incidental findings". Most incidental findings have no significant health consequences, but in a small percentage of cases further evaluation or treatment may be indicated. If an incidental finding is noted in any image data, we will consult with experts, and it might be recommended that the participant obtain a full clinical MRI scan. It will then be up to the participant to

pursue it with your physician. Although study personnel may be able to provide some advice, the decision of whether and how to pursue an incidental finding can only be made by the participant's physician who has knowledge of her medical history.

Use of venipuncture for blood sampling: Inserting a needle into a vein is safe when done by professionals under clean conditions. Sometimes a bruise will occur at the puncture site and on rare occasions fainting, a blood clot, or an infection may form in the vein. If this occurs, appropriate treatment will be instituted immediately.

Behavioral Assessments: Subjects may feel upset when answering questions on the TLEQ and ACE. Should a subject report or appear distressed about the feelings that arise from answering these questions, then arrangements will be made for the subject to see the study doctor for an assessment immediately. All subjects reporting significant distress, homocidality, or suicidality, will be evaluated by a trained psychiatrist (P.I. and co-P.I.) and a decision about emergency treatment versus referral will be made. If participants opt to complete the ACE over the phone and experience distress the same arrangements will be made for participants to speak with a study doctor about their distress.

Nonspecific risks: As a result of their participation in these studies, subjects will have more blood drawn than would be the case in usual clinical practice. The maximal amount of blood subjects will have drawn will be less than one blood donation (85 cc), spread out over a period of 1-8 weeks.

# 2. Benefits

A better understanding of the effects of estrogen on 5-HT function, mood, and cognition is a potential benefit to the society at large. In light of the recent findings from the Women's Health Initiative it is particularly important that we begin to clarify who should receive estrogen treatment (peri and/or postmenopausal women) and what kind of cognitive and mood benefits can be expected from such treatment. Knowledge of the impact of ovarian hormones on brain function is important to understanding and treating menopausal symptoms.

Another potential benefit is that subjects will receive ERT and an extensive psychiatric and medical evaluation.

#### 3. Subject Confidentiality

How will confidentiality of data be maintained? Check all that apply.

Paper-based records will be kept in a secure location and only be accessible to personnel involved in the
study.
Computer-based files will only be made available to personnel involved in the study through the use of
access privileges and passwords.

Prior to access to any study-related information, personnel will be required to sign statements agreeing to protect the security and confidentiality of identifiable information.

$\boxtimes$	Whenever feasible,	identifiers will be	removed from stud	y-related information.

A Certificate of Confidentiality will be obtained, because the research could place the subject at risk of criminal or civil liability or cause damage to the subject's financial standing, employability, or liability.

A waiver of documentation of con	sent is being r	equested, b	because the on	ly link between th	e subject and
the study would be the consent do	cument and th	ne primary r	isk is a breach	of confidentiality.	(This is not an
option for FDA-regulated research	.)				

Precautions are in place t	o ensure the data i	is secure by usin	g passwords a	nd encryption,	because the
research involves web-bas	sed surveys.				

Audio and/or video	recordings will be trans	cribed and then d	estroyed to eliminate	e audible identification of
subjects.	-		-	

Other (specify):

All of the information obtained from subjects is quoted by number and kept in locked confidential files. Any identifiable information that is obtained in connection with this study will remain confidential and will be disclosed only with the subject's permission or as required by U.S. or State law. Examples of information that we are legally required to disclose include abuse of a child or elderly person, or certain reportable diseases. This information is not available to anyone except the investigators and is not identified by the subject's name. The subject's clinical records are protected by the procedures of University of Pennsylvania School of Medicine. The investigators and anyone else involved with this project will not be allowed to reveal any identifying characteristics about the patients who participate in this study without their written consent. In the case of published reports from this study, care will be taken so that no individual subject will be identifiable.

Representatives from the Penn Office of Human Research may inspect study records during internal auditing procedures. However, these individuals are required to keep all information confidential. The U.S. Food and Drug Administration (FDA) and National Institutes of Health may also inspect study records during external auditing procedures. These individuals are also required to keep all information confidential.

